3.15 Guidelines for Dose Modifications and Toxicity Management for Combination Therapy

If treatment related toxicities occur when dabrafenib is used in combination with trametinib then both treatments should be simultaneously dose reduced, interrupted or discontinued with the exception shown below:

- Dose modification is necessary for only dabrafenib
 - Mild to moderate pyrexia ([Section 3.15.1](#))
 - Uveitis ([Section 3.13.5](#) and [Section 3.14](#))
- Dose modifications are necessary for only trametinib:
 - Retinal vein occlusions (RVO) and retinal pigment epithelial detachment (RPED) ([Section 3.13.5](#))
 - Left ventricular ejection fraction (LVEF) reduction (asymptomatic, [Section 3.12.3.1](#))
 - Pneumonitis and interstitial lung disease (ILD) (grade 4, [Section 3.13.7](#))

The severity of adverse events (AEs) will be graded utilizing the NCI-CTCAE v4.03 ([NCI 2009](#)). Guidelines for dose modifications and interruptions for management of common toxicities associated with dabrafenib are provided in this section.

Trametinib dose reduction for patients enrolled in all parts of the study should follow dose reduction column in the trametinib dosing nomogram in Appendix 2.

Dabrafenib dose reduction should follow the dose reduction column in the dabrafenib dosing nomogram in Appendix 2 provided for patients enrolled in Part C and Part D, as described below

- Dabrafenib dose modification levels in Part C
 - If a subject is dosed at Dose Level 1, and requires dose reduction, treatment must be discontinued
 - If a subject is dosed at Dose Level 2, and requires dose reduction, follow the dose reduction column in dosing nomogram
- Dabrafenib dose modification levels in Part D.
 - Follow dose reduction column in dosing nomogram

Nomograms for each dosing level are provided in [Appendix 2](#).

If a second dose reduction is required, the treatment should be discontinued.

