In patients who received the combination dose of dabrafenib in combination with trametinib, cutaneous SCC (including keratoacanthoma [KA]) occurred in a lower percentage of subjects and events occurred later than with dabrafenib monotherapy, with the median time to onset of the first occurrence of 20 to 32 weeks as compared to approximately 8 weeks with dabrafenib monotherapy. Most patients on combination therapy who developed cuSCC continued on dabrafenib treatment without dose modification. Skin examination should be performed prior to initiation of dabrafenib and during treatment with dabrafenib, every 2 months throughout therapy. An additional examination should be considered 2 to 3 months after discontinuation of dabrafenib or until initiation of another anti-neoplastic therapy. Cases of cuSCC should be managed by dermatological excision and dabrafenib treatment should be continued without any dose adjustment. Patients should be instructed to immediately inform their physician if new skin lesions develop.

New primary melanoma: New primary melanomas have been reported in patients treated with dabrafenib. These were identified within the first 5 months of therapy and did not require treatment modification other than excision. Monitoring for skin lesions should occur as described for cuSCC.

Rash: Skin-related toxicities, primarily rash (maculopapular type rash with dabrafenib and acneiform-type rash with trametinib) have been reported with both trametinib and dabrafenib monotherapies. The incidence of skin-related events reported with the combination regimen appears to be lower than what has been observed following trametinib monotherapy. Rash management guidelines are provided in [Section 3.13.3](#).

Hemorrhage: Major hemorrhagic events including fatal events can occur in patients receiving dabrafenib in combination with trametinib. Monitor for signs and symptoms of bleeding.

Venous Thromboembolism: Deep vein thrombosis and pulmonary embolism can occur in patients receiving dabrafenib in combination with trametinib.

Interstitial lung disease (ILD)/Pneumonitis:

Pneumonitis has been observed in subjects receiving trametinib and trametinib in combination with dabrafenib. To reduce the risk of pneumonitis, subjects will be monitored closely for symptoms, evaluated with imaging and functional tests if clinically indicated. No modification of dabrafenib is required when taken in combination with trametinib.

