3.13 Dose Delay and Modification for Events Considered Related to Trametinib

A maximum of one trametinib dose reduction is allowed. If a second dose level reduction is required, treatment will be permanently discontinued.

Trametinib dose modification guidelines are outlined in [Table 3-6](#) for clinically significant toxicities with exception for following events of special interest:

- rash ([Section 3.13.3](#))
- diarrhea ([Section 3.13.4](#))
- ejection fraction changes ([Section 3.12.3.1](#))
- hypertension ([Section 3.13.5](#))
- prolonged QTc ([Section 3.12.1](#))
- pneumonitis ([Section 3.13.5](#))
- visual changes ([Section 3.13.5](#))
- liver chemistry elevation ([Section 3.12.1](#))

For these refer to the relevant sections for dose modification guidelines for adverse events of special interest as stated above.

If treatment related toxicities occur when dabrafenib is used in combination with trametinib then both treatments should be simultaneously dose reduced, interrupted or discontinued with the exceptions described below.

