3.13.7 Pneumonitis

Pneumonitis has been observed in subjects receiving trametinib. To reduce the risk of pneumonitis, subjects will be monitored closely for symptoms, evaluated with imaging and functional tests if clinically indicated. Dose modification and supportive care guidelines for pneumonitis are described in [Table 3-11](#).

Table 3-11 Mandatory dose modifications and recommended clinical management guidelines for pneumonitis

CTCAE v4.03 Grade	Recommended adverse event management guidelines	Mandatory dose modification requirements
Grade 1	
 • CT scan (high-resolution with lung windows) • Clinical evaluation and laboratory work-up for infection • Monitoring of oxygenation via pulse-oximetry • Consultation with pulmonologist 	
 • Continue study treatment (s) at current dose
Grade 2	
 • CT scan (high-resolution with lung windows) • Clinical evaluation and laboratory work-up for infection • Consult pulmonologist • If feasible, pulmonary function tests -if <normal, repeat every 8 weeks until \geqnormal • Bronchoscopy with biopsy and/or BAL • Symptomatic therapy including corticosteroids if clinically indicated 	
 • Interrupt trametinib until recovery to grade \leq1 (on combination therapy, dabrafenib may continue) • Restart treatment with reduced trametinib dose level (Appendix 2, dose reduction column) • Escalation to previous dose level after 4 weeks if a period of 4 weeks of treatment have passed since restarting dosing at the lower dose level and there is no recurrence of the AE • If no recovery to grade \leq1 within 4 weeks, permanently discontinue trametinib (on combination therapy, dabrafenib may continue)

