Grade 3	
 • CT scan (high-resolution with lung windows) • Clinical evaluation and laboratory work-up for infection • Consult pulmonologist • If feasible, pulmonary function tests-if <normal, repeat every 8 weeks until \geqnormal • Bronchoscopy with biopsy and/or BAL if possible • Symptomatic therapy including corticosteroids as clinically indicated 	
 • Interrupt trametinib until recovery to grade \leq1 (on combination therapy, dabrafenib may continue) • When recovered to grade \leq1, treatment with trametinib may be restarted at reduced dose (Appendix 2, dose reduction column) • If no recovery to grade \leq1 within 4 weeks, permanently discontinue trametinib (on combination therapy, dabrafenib may continue)
Grade 4	
 • Same as grade 3 	
 • Permanently discontinue trametinib (on combination therapy, dabrafenib may continue)

Abbreviations: BAL= bronchioalveolar lavage; CT = computed tomography; CTCAE = Common Terminology Criteria for Adverse Events
		

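### Section 3.15 limits the trametinib-only rule for pneumonitis/ILD to grade 4, while the mandatory column of Table 3-11 lets dabrafenib continue at Grades 2, 3 and 4

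*Protocol*

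**What the plan says.** Protocol Section 3.15 sets the default for children on trametinib plus dabrafenib. For treatment-related toxicity, "both treatments should be simultaneously dose reduced, interrupted or discontinued with the exception shown below". One list of exceptions names events where only dabrafenib changes, and a second names events where only trametinib changes. The second list includes "Pneumonitis and interstitial lung disease (ILD) (grade 4", with a reference to Section 3.13.7.

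Section 3.13.7 contains Table 3-11, whose dose-modification column is headed as mandatory. At Grade 2 and at Grade 3 it interrupts trametinib and lets dabrafenib continue. If trametinib is resumed, the text concerns trametinib only: "Restart treatment with reduced trametinib dose level" at Grade 2 and "treatment with trametinib may be restarted at reduced dose" at Grade 3. If there is no recovery to Grade 1 or better, both rows end "within 4 weeks, permanently discontinue trametinib (on combination therapy, dabrafenib may continue". Grade 4 has the same allowance: "permanently discontinue trametinib (on combination therapy, dabrafenib may continue".

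Section 1.7.2, under ILD/pneumonitis, says "No modification of dabrafenib is required when taken in combination with trametinib" and gives no grade. Section 3.13 has its own both-drugs default, worded more openly: "both treatments should be simultaneously dose reduced, interrupted or discontinued with the exceptions described below". It lists pneumonitis among the events of special interest that have their own section, but the pointer goes to 3.13.5, which is Hypertension.

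**The concern.** Two current dosing instructions for the same event disagree. Section 3.15 exempts dabrafenib at grade 4 only, which leaves Grades 2 and 3 under the rule that both drugs move together. The table it cites exempts dabrafenib at all three grades. Taken literally, 3.15 also gives an odd ordering, with dabrafenib handled more strictly for moderate or severe pneumonitis than for life-threatening pneumonitis.

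What is at stake is whether a Part C or Part D child with a BRAF V600 tumour has dabrafenib interrupted or reduced when the table does not call for it. In the other direction, a site that follows the table departs from 3.15 as written.

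**Working it through.** There is no figure to reproduce, so the check is a comparison of texts, grade by grade, for dabrafenib on combination therapy.

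| Grade | 3.15 read literally | Table 3-11, mandatory column | Agreement |
|---|---|---|---|
| 1 | No modification triggered | Both drugs continue at current dose | Yes |
| 2 | Dabrafenib modified with trametinib | Trametinib interrupted; dabrafenib may continue | No |
| 3 | Dabrafenib modified with trametinib | Trametinib interrupted; dabrafenib may continue | No |
| 4 | Trametinib only | Trametinib stopped; dabrafenib may continue | Yes |

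Section 1.7.2 has no grade limit, so it fits the table in every row. It is risk background rather than an operative dosing rule, so it supports the table but does not decide the matter.

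**Could the grade be only an illustration?** The neighbouring LVEF entry in 3.15 is qualified as asymptomatic, and that qualifier does restrict. Table 3-5 lets dabrafenib continue for an asymptomatic decrease but interrupts it for a symptomatic one. A reader would naturally take the pneumonitis qualifier the same way.

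**What a literal reading of 3.15 does.**
- Interruption or reduction of dabrafenib is usually reversible: Sections 3.7.3, 3.7.4 and 3.14 allow re-escalation.
- The exception is Part C Dose Level 1. Section 3.15 and the Appendix 2 footnote allow no dabrafenib reduction there, so a child who requires one must stop. Section 3.7.3 let such children move to Dose Level 2 after at least 56 days if they met its other conditions. The protocol does not say how many, if any, remain on Dose Level 1.

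**Does a DLT count move?** Section 3.2.3.1 counts Grade 2 pneumonitis as a DLT in its own right, and Grade 3 or 4 falls under the general non-hematological rule. Section 12.3.1 keeps any subject with a DLT in the DLT-evaluable population whatever the exposure. How dabrafenib is handled afterwards changes neither.

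**How many children?** Parts C and D enrolled 18 + 30 = 48. Across all parts, 139 - 80 = 59 had not discontinued by 17-Jul-2020, or 59 - 13 = 46 if the 13 rollover children are not among the 80. The documents do not split the discontinuations by part and give no count of pneumonitis cases on combination therapy.

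**The case against.** The best reply is that the protocol already shows which text to follow. Section 3.13 sends pneumonitis to its own section and allows exceptions set out below it, and Table 3-11 is below it. The table's column is mandatory, whereas 3.15 is a guideline worded as advice. The 3.15 bullet itself refers to 3.13.7. This largely stands, and most sites would probably follow the table. A reader might infer that the protocol leaves sites with no way to choose; these cross-references do not support that. They do not remove the express grade 4 limit, however, and the pneumonitis pointer in 3.13 leads to the wrong section.

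It is also fair to say that the table is permissive. Dabrafenib may continue but need not, so a site that interrupts both drugs breaches neither text. Section 3.14 asks for clinical judgement and caution. The strict clash is therefore one-way: continuing dabrafenib at Grade 2 or 3 follows the table and departs from 3.15.

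A reader might go further and infer that 3.15 would cost a child dabrafenib for good whenever Grade 2-3 pneumonitis has not resolved in 4 weeks, because Section 6.3 bars retreatment. The documents do not support that. The 4-week pneumonitis rule is in Table 3-11, and the same bullet says dabrafenib may continue; a site would have to apply the trigger and ignore the allowance attached to it. The separate route in 6.3, a toxicity delay of more than 28 days, is worded as something that may lead to discontinuation.

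**Conclusion.** The point holds as a minor correction to text that is wrong as written. Section 3.15 contradicts the mandatory column of Table 3-11 at Grades 2 and 3, and both the table and 1.7.2 show which way to correct it. The practical risk is needless interruption or reduction of dabrafenib at a site that applies 3.15 literally. That is usually reversible, but not for any child still on Part C Dose Level 1 who requires a reduction.

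The number affected is unknown and may be zero. Figures of 48 or 46 might be read as a count of children at risk, but the documents do not support that. They only cap how many could still have been on combination treatment, and 48 sits badly with discontinuations reported across all four parts. The remaining time may also be short: all cohorts were closed by Amendment 9, and 6.5 asks for a minimum of 6 months after the last enrolment.

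No DLT count, endpoint or statistical figure changes. The conclusion rests on reading the grade qualifier in 3.15 as a limit, as its LVEF neighbour is.

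**What to change.** In Section 3.15, change the qualifier on the pneumonitis/ILD entry from grade 4 to Grades 2-4 and keep the reference to 3.13.7. In Section 3.13, change the pneumonitis pointer from 3.13.5 to 3.13.7. Tell sites with Part C or Part D subjects still on treatment that Table 3-11 applies.

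The cost is a short text edit and a site letter, possibly with IRB/IEC approval: Amendment 8, which changed dose-modification rules, required approval before implementation. No new data collection or reanalysis is needed.

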3.13.1 Dose Delay and Modification for Events Considered Related to Trametinib and/or Dabrafenib

Table 3-6 Dose Delay and Modification for General Events Considered Related to Trametinib and/or Dabrafenib

CTCAE Grade	Recommended adverse event management guidelines	Mandatory dose modification requirements
Grade 1 and tolerable Grade 2	
 • Monitor closely • Provide supporting care according to institutional standards 	
 • Continue study drug(s) at current dose level
Intolerable Grade 2 and Grade 3	
 • Monitor closely. • Provide supportive care according to institutional standards. 	
 • Interrupt study drug(s) (except for cuSCC, keratoacanthoma, new primary melanoma, and basal cell carcinoma) • When toxicity resolves to Grade 1 or baseline, restart study drug(s) at reduced levels (see Appendix 2 dosing nomogram "Dose Reduction" columns for trametinib and dabrafenib) • If the Grade 2 (intolerable) or Grade 3 toxicity recurs while at reduced dose, discontinue study treatment(s) • If the Grade 2 (intolerable) or Grade 3 toxicity recurs while after re-escalating to previous dose,

CTCAE Grade	Recommended adverse event management guidelines	Mandatory dose modification requirements
		
 Interrupt dabrafenib and trametinib. When toxicity resolves to Grade 1 or baseline, restart study drug(s) reduced levels (see Appendix 2 dosing nomogram "Dose Reduction" columns for trametinib and dabrafenib)
Grade 4	
 Monitor closely. Provide supportive care according to institutional standards. 	
 Interrupt study drug (s) Once toxicity resolves to \leq Grade 1 or baseline, restart study drug(s) at reduced levels (see Appendix 2 dosing nomogram "Dose Reduction" columns for trametinib and dabrafenib) or permanently discontinue study drug (s) at the discretion of investigator

Table 3-6a Dose Modification for dabrafenib (DRB436) dispersible tablet for patients less than 12 years of age

Weight (kg)	Dose (b.i.d)	Dose Reduction Level 1 (b.i.d)	Dose Reduction Level 2 (b.i.d)
7-9.5	20 mg	10 mg	0 mg
9.6-13.5	30 mg	20 mg	10 mg
13.6-17.5	40 mg	30 mg	20 mg
17.6-20.5	50 mg	40 mg	30 mg
20.6-24.5	60 mg	50 mg	40 mg
24.6-28.5	70 mg	60 mg	50 mg
28.6-32.5	80 mg	70 mg	60 mg
32.6-36.5	90 mg	80 mg	70 mg
36.6-40.5	100 mg	90 mg	80 mg
40.6-43.5	110 mg	100 mg	90 mg

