43.6-47.5	120 mg	110 mg	100 mg
47.6-51.5	130 mg	120 mg	110 mg
51.6-55.5	140 mg	130 mg	120 mg
\geq 55.6 kg	150 mg	140 mg	130 mg
Dose: 5.25 mg/kg/day Dose level 1: 4.5 mg/kg/day Dose level 2: 3.75 mg/kg/day			

Table 3-6b Dose Modification for dabrafenib (DRB436) dispersible tablet for patients greater or equal 12 years of age

Weight	Dose (b.i.d)	Dose Reduction Level 1 (b.i.d)	Dose Reduction Level 2 (b.i.d)
10-11.5	20 mg	10 mg	0 mg
11.6-17.5	30 mg	20 mg	10 mg
17.6-20.5	40 mg	30 mg	20 mg
20.6-24.5	50 mg	40 mg	30 mg
24.6-28.5	60 mg	50 mg	40 mg
28.6-32.5	70 mg	60 mg	50 mg
32.6-36.5	80 mg	70 mg	50 mg

36.6-40.5	90 mg	80 mg	60 mg
40.6-43.5	100 mg	90 mg	60 mg
43.6-47.5	110 mg	100 mg	70 mg
47.6-51.5	120 mg	110 mg	80 mg
51.6-55.5	130 mg	120 mg	80 mg
55.6-64.5	140 mg	130 mg	100 mg
≥64.6	150 mg	140 mg	110 mg
Dose: 4.5 mg/kg/day Dose level 1: 3.75 mg/kg/day Dose level 2: 3.00 mg/kg/day			

For subjects treated with solid dosage forms, dose reductions will occur in increments of 50 mg from the total daily dose for dabrafenib capsules and in increments of 0.5 mg from the total daily dose for trametinib tablets. See also [Appendix 2](#).

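### Tables 3-6a and 3-6b print a second dabrafenib dose reduction for dispersible tablets, while Section 3.15 discontinues treatment when a second reduction is needed

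*Protocol*

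**What the plan says.** Section 3.15 sets the dose-modification rules for the combination. On dabrafenib in Parts C and D it says: "Dabrafenib dose reduction should follow the dose reduction column in the dabrafenib dosing nomogram in Appendix 2". For Part C subjects on the half-dose starting level it adds: "If a subject is dosed at Dose Level 1, and requires dose reduction, treatment must be discontinued". Straight after the dabrafenib bullets and a pointer to the nomograms comes the general rule: "If a second dose reduction is required, the treatment should be discontinued".

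Section 3.13.1 holds three tables. Table 3-6 gives the general toxicity rules. It interrupts for intolerable Grade 2 or Grade 3 events, restarts at a reduced level, and discontinues if the toxicity returns at that level. Table 3-6a is titled "Dose Modification for dabrafenib (DRB436) dispersible tablet for patients less than 12 years of age" and Table 3-6b "Dose Modification for dabrafenib (DRB436) dispersible tablet for patients greater or equal 12 years of age". Both have a column whose heading begins "Dose Reduction Level 2 (b.i.d". Their footers give the matching mg/kg levels; in Table 3-6a the last is "Dose level 2: 3.75 mg/kg/day".

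In Appendix 2, each full-dose capsule nomogram refers the reader to the next lower capsule nomogram and no further. Section 3.11.2 requires dispersible tablets for children under 6 and for anyone at risk of choking on capsules. Section 4.2.2 adds weight limits below which they are also required.

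**The concern.** Take a child on full-dose dabrafenib dispersible tablets who has been reduced once and now needs another reduction. Under Section 3.15 treatment ends. A reader of Table 3-6a or 3-6b finds a lower dose printed for that child's weight. Nothing in the protocol ties the second column to a particular event, study part or subgroup, or exempts it from Section 3.15.

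This matters for the results as well as for conduct. Section 3.9.4 names safety and tolerability as the primary endpoints of Part D. Section 12.5.2.2 gives adverse events leading to discontinuation their own summary, and Section 6.3 bars retreatment after permanent discontinuation. If sites resolve the conflict differently, part of the discontinuation count reflects which page was followed. The formulation rule means that any such effect would be concentrated in the youngest children.

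**Working it through.** No sample size, power or error rate is involved. The check compares the texts and counts the weight bands.

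**1. How many dabrafenib steps down each place allows**

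| Place | Steps down from full dose |
|---|---|
| Section 3.15 | One; a second leads to discontinuation |
| Table 3-6 | One for a given toxicity; recurrence of intolerable Grade 2 or Grade 3 at the reduced dose leads to discontinuation |
| Appendix 2, capsules, under 12 years | One: 5.25 to 4.5 mg/kg/day, referring only to the dose column of the lower nomogram |
| Appendix 2, capsules, 12 years and over | One: 4.5 to 3.75 mg/kg/day |
| Table 3-6a, dispersible tablets, under 12 years | Two: 5.25 to 4.5 to 3.75 mg/kg/day |
| Table 3-6b, dispersible tablets, 12 years and over | Two: 4.5 to 3.75 to 3.00 mg/kg/day |

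**2. In how many weight bands the conflict is real**

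- Table 3-6a has 14 bands. Level 2 is 0 mg in the 7-9.5 kg band and runs from 10 to 130 mg twice daily in the rest: 14 − 1 = 13 bands.
- Table 3-6b has 14 bands. Level 2 is 0 mg in the 10-11.5 kg band and runs from 10 to 110 mg twice daily in the rest: 14 − 1 = 13 bands.
- Together, 13 + 13 = 26 of 28 bands conflict. In the other two, 0 mg stops dabrafenib, as Section 3.15 does.

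**3. One row as an illustration**

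A child under 12 weighing 20 kg falls in the 17.6-20.5 kg band of Table 3-6a: 50, then 40, then 30 mg twice daily. If a second reduction is needed, the table shows 30 mg twice daily and Section 3.15 discontinues.

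**4. Who is exposed**

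- Part C Dose Level 1 subjects (2.63 or 2.25 mg/kg/day, Table 3-4) are outside the conflict while on that dose, because their own rule discontinues at the first reduction.
- That leaves full-dose subjects on dispersible tablets in Parts C and D. The Amendment 9 rationale reports 18 and 30 enrolled in these parts, so 18 + 30 = 48 is a ceiling for the whole of both parts. The affected number is smaller by an amount the protocol does not give.
- A second reduction can arise. In Table 3-12 a first fever above 40°C and, separately, later fevers each lead to restarting dabrafenib at a lower dose.

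**5. Labels**

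The footers of Tables 3-6a and 3-6b call the reduced doses Dose level 1 (4.5 or 3.75 mg/kg/day) and Dose level 2 (3.75 or 3.00). In Table 3-4 those names mean the Part C starting dose (2.63 or 2.25) and the full dose (5.25 or 4.5).

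**The case against.** The strongest reply is that Tables 3-6a and 3-6b are look-up tables with no trigger. No sentence tells anyone to move to Level 2. Section 3.15 does not mention these tables, and both it and Table 3-6 send reductions to Appendix 2. On this view the operative text points one way, and the second column is merely unexplained. That stands in part: it is fair not to call the tables a competing rule. But they are titled as dose-modification tables, print usable doses and sit in the section on dose modification. Section 3.14 also speaks of re-escalating through the same steps as de-escalation, so a site could reasonably think that more than one step exists.

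Three readings that would remove the conflict do not work:

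- *Section 3.15 means trametinib only.* Its sentence follows the dabrafenib bullets, and the trametinib limit has its own statement in Section 3.13.
- *Level 2 is for dabrafenib given alone.* No part of the study starts dabrafenib alone. Some subjects may continue it after trametinib stops, but no text links Level 2 to them.
- *Level 2 means stopping.* This fits only the two 0 mg bands.

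A reader might also infer more than the protocol supports. Section 3.13 says "A maximum of one trametinib dose reduction is allowed"; that concerns trametinib and is no evidence of a dabrafenib limit. Nor does the conflict reach all 28 bands or every dispersible-tablet subject. The label overlap is a lesser matter, since the column headings say reduction and the footers print the mg/kg values.

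**Conclusion.** The protocol is internally inconsistent on whether a second dabrafenib reduction exists for dispersible tablets. The case rests on Section 3.15, supported by Table 3-6 and the one-step capsule nomograms, against Tables 3-6a and 3-6b.

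The practical weight is modest. All cohorts are closed to enrollment, Part D tests no hypothesis, and the discontinuation summary is descriptive. It would be tempting to conclude that discontinuation rates have been distorted or that sites have treated like children differently. Nothing in the protocol shows that either happened. What is established is a conflicting instruction that could produce such differences.

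The conclusion assumes that the word treatment in the Section 3.15 rule includes dabrafenib, as its position suggests. The text available for review breaks off within the Appendix 2 dispersible-tablet nomogram, so nothing here depends on what that nomogram says about reductions. No view is taken on which rule is clinically right.

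**What to change.** Reconcile Section 3.15, Table 3-6, Tables 3-6a/3-6b and Appendix 2 on whether a second dabrafenib reduction exists for dispersible tablets, as the clinical team decides. If the Level 2 column is kept, state when it applies and how it relates to Section 3.15. As a minor editorial step, rename the dose levels in the footers of Tables 3-6a and 3-6b so that they cannot be taken for Part C Dose Levels 1 and 2.

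In reporting, at most describe the dabrafenib discontinuations that followed a recorded first reduction. Section 4.4 and Table 7-4 already provide for recording dose reductions, and Section 6.3 for the primary reason for discontinuation. Flagging discontinuations that followed a request for a second reduction would not be feasible, because the protocol does not describe recording requests.

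The cost is a clarification letter or amendment and, if wanted, one descriptive listing from existing data.
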